3.2. Inclusion Criteria

Potential subjects must satisfy all of the following criteria to be enrolled in the study:

1. The subject must read, understand, and sign the STATEMENT OF INFORMED CONSENT and receive a fully executed copy of the form
2. Appear able and willing to adhere to the instructions set forth in this clinical protocol
3. Between 18 and 35 (inclusive) years of age at the time of screening
4. The subject must be habitual contact lens wearers (defined as minimum 6 hours per day, 5 days a week over the last month)
5. The subject must meet all of the following three criteria:
 - a. The eye's spherical equivalent distance refraction must be in the range of -1.00 to -9.00 D (inclusive).
 - b. The eye's refractive cylinder must be less than or equal to -0.75 DC.
 - c. Each eye must have best corrected visual acuity of 20/25 or better.
6. The subject must have normal eyes (i.e., no ocular medications or infections of any type)

3.3. Exclusion Criteria

Potential subjects who meet any of the following criteria will be excluded from participating in the study:

1. Currently pregnant or lactating
2. Any systemic disease (e.g., Sjögren's Syndrome), allergies, infectious disease (e.g., hepatitis, tuberculosis), contagious immunosuppressive diseases (e.g., HIV), autoimmune disease (e.g. rheumatoid arthritis), or other diseases, by self-report, which are known to interfere with contact lens wear and/or participation in the study
3. Use of systemic medications (e.g., chronic steroid use) that are known to interfere with contact lens wear or may impact the functioning of the tear film (e.g., Isotretinoin)
4. Any ocular allergies, infections or other ocular abnormalities that are known to interfere with contact lens wear and/or participation in the study. This may include, but not be limited to entropion, ectropion, extrusions, chalazia, recurrent styes, glaucoma, history of recurrent corneal erosions, aphakia, or corneal distortion
5. Any current use of ocular medication
6. Any previous, or planned (during the course of the study) ocular surgery (e.g., radial keratotomy, PRK, LASIK, etc.)
7. Any Grade 3 or greater slit lamp findings (e.g., edema, corneal neovascularization, corneal staining, tarsal abnormalities, conjunctival injection) on the Efron scale
8. Any previous history or signs of a contact lens-related corneal inflammatory event (e.g., past peripheral ulcer or round peripheral scar), or any other ocular abnormality that would contraindicate contact lens wear
9. Any known hypersensitivity or allergic reaction to contact lens care products.
10. Participation in any contact lens or lens care product clinical trial within 30 days prior to study enrollment
11. Employee of clinical site (e.g., Investigator, Coordinator, Technician)
12. Current wearers of AO1D brand contact lenses

3.4. Enrollment Strategy

Study subjects will be recruited from the clinical site's subject database and/or utilizing Independent Ethics Committee (IEC) or Institutional Review Board (IRB) approved materials.

4. STUDY DESIGN AND RATIONALE

4.1. Description of Study Design

This is a bilateral, non-dispensing, randomized-controlled, cross-over, single masked, single-site study. There will be a total of 3 visits and the study endpoints will be measured in all subjects at baseline with habitual lenses and under the two testing treatments (AO1D, SCR) sequentially in separate visits based on the randomization scheme.

NB: use of ocular lubricating drops are not allowed in this study.

4.2. Study Design Rationale

Subjects in this study will serve as their own control in a 2x2 crossover design. The study endpoints will be sequentially measured in each of the 2 post screening visits under the 2 different treatments based on the randomization scheme.

4.3. Enrollment Target and Study Duration

- 45 subjects will be enrolled with the aim of completing at least 42
- Single-site, internal clinical trial
- The study will include 3 visits. The first visit will be the screening and baseline visit. Subsequent visits will include testing under the 2 treatments: AO1D, SCR based on the randomization scheme. Enrollment period will be approximately 3-4 weeks.

5. TEST ARTICLE ALLOCATION AND MASKING

5.1. Test Article Allocation

The study lenses will be worn in a bilateral and random fashion using a 2x2 design. Permuted block randomization will be used to minimize the potential for bias in treatment allocation and to enhance validity of statistical comparisons across treatment groups. The randomization is such that on completion of the study visits each subject will have been tested under the 2 different treatments: AO1D, SCR. The subject will only be tested under a single treatment at each visit. The clinical site will follow the randomization scheme provided and will complete enrollment according to the randomization list and will not pre-select or assign subjects.

5.2. Masking

This study is single masked. Masking will be used to reduce potential bias. Subjects will be *unaware* of the identity of the investigational product. Contact lenses in the study will be over-labeled to reduce subject exposure to test product brand.

Under normal circumstances, the mask should not be broken until all subjects have completed the study and the database is finalized. Otherwise, the mask should be broken only if specific emergency treatment/course of action would be dictated by knowing the treatment status of the subject. In such cases, the Investigator may, in an emergency, contact the medical monitor. In the event the mask is broken, the Sponsor must be informed as soon as possible. The date, time, and reason for the unmasking must be documented in the subject record. The Investigator is also advised not to reveal the study treatment assignment to the clinical site or Sponsor personnel.

Subjects who have had their treatment assignment unmasked are expected to return for all remaining scheduled evaluations. Subjects who are discontinued during the enrolment period will be replaced. Once enrolment is completed, no further replacements will be allowed.

5.3. Procedures for Maintaining and Breaking Randomization Codes

The test articles mask shall not be broken unless information concerning the lens type is necessary for the urgent medical treatment of a subject. The Sponsor must be notified before the mask is broken.

6. STUDY INTERVENTION

6.1. Identity of Test Articles

The following contact lenses will be used in this study:

Table 1: Test Articles

	Test	Control
Test Article Form	Soft Contact Lens (best spherical equivalent)	Trial Frame of best corrected spherocylindrical refraction
Lens Name	ACUVUE OASYS® 1-Day with HydraLuxe™	NA
Product Type	Marketed	NA
Manufacturer	Johnson & Johnson Vision Care, Inc.	NA
Packaging Form	Blister Pack	NA
Lens Production Protocol Number	N/A	NA
Nominal Distance Powers	-1.00 to -6.00D in 0.25D steps and - 6.50 to -9.00 in .50D steps	As refracted on the day of visit
Material / main component of formulation	senofilcon A	NA
Nominal Water content (%)	38%	NA
Nominal Base Curve/Diameter Range @ 22°C (mm)	8.5/14.3	NA

There will be 2 lenses (one pair per subject) of AO1D used in this study. Therefore, for the 45 subjects in this study and giving room for lens replacements, approximately 100 lenses will be used.

6.2. Ancillary Supplies/Products

[figure not shown]
There should be no solutions used in this study.

6.3. Administration of Test Articles

Test articles will be fitted to subject meeting all eligibility requirements. Damaged test articles will be replaced at the discretion of the Investigator and/or the Sponsor.

6.4. Packaging and Labeling

The test articles will be packaged in blisters as the primary packaging. The test article will be over-labeled to mask the subject to the identity of the lens. The test articles will be in plastic bags as the secondary packaging form. The sample study label is shown below:

6.5. Storage Conditions

Test articles will be maintained at ambient temperatures at the clinical site. Test articles must be kept under secure conditions.

6.6. Collection and Storage of Samples

No samples will be collected as part of the study procedures.

When possible, any lens or test article associated with an Adverse Events and/or a Product Quality Complaint must be retained and stored in a glass vial with moderate solution pending directions from the sponsor for potential return back to JJVC.

6.7. Accountability of Test Articles

JJVC will provide the Investigator with sufficient quantities of study articles and supplies to complete the investigation. The Investigator is asked to retain all lens shipment documentation for the test article accountability records.

Test article must be kept in a locked storage cabinet, accessible only to those assigned by the Investigator for dispensing. The Investigator may delegate this activity to authorized study site personnel listed on the Site Delegation Log. All test articles must be accounted. This includes:

1. What was dispensed for the subject for trial fitting, to wear out of the office, or issued for the subject to replace appropriately between visits
2. What was returned to the Investigator unused
3. The number and reason for unplanned replacements.

The Investigator will collect all unused test articles from the subjects at the end of the subject's participation. Subject returned unused test articles must be separated from the clinical study inventory of un-dispensed test articles, and must be labeled with the subject number and date of return. Following final reconciliation of test articles by the monitor, the Investigator or monitor will package and return all unused test articles to JJVC.

If there is a discrepancy between the shipment documents and the contents, contact the study monitor immediately.

Reference [REDACTED] Site Instructions for Test Article Receipt and Test Article Accountability for additional information.

7. STUDY EVALUATIONS

7.1. Time and Event Schedule

Table 2: Time and Events

Event	Visit 1 Day 0 (habitual lenses)	Visit 2 2(±1) Day after V1	Visit 3 2(±1) Day after V2	Final Evaluation
Estimated Visit Duration	2 hours	2 hours	2 hours	20 minutes
Statement of Informed Consent	X			
Demographics	X			
Medical History and Concomitant Medications	X			
Change of Medical History and Concomitant Medications		X	X	
Eligibility (Inclusion/Exclusion Criteria including baseline)	X			
Continuance of Eligibility*	X	X	X	
Entrance Visual Acuity (Electronic LogMAR)	X	X	X	
Exit Visual Acuity (Electronic LogMAR)	X	X	X	X
Subjective Sphero-cylindrical Refraction	X			X
Subjective Best-sphere Refraction	X			
Entrance Slit Lamp Biomicroscopy	X	X	X	
Exit Slit Lamp Biomicroscopy (if applicable)	X	X	X	X
Randomization For Testing treatment		X		
Lens Fitting/Settling (if applicable)	X	X		
Subjective Lens Fit Assessment (if applicable)	X	X	X	
Lens Power Modification (if applicable)	X	X	X	
Distance ETDRS Electronic LogMAR Visual Acuity	X	X	X	
Contrast Sensitivity Testing (qCSF)	X	X	X	
Tear Film Interferometry	X	X	X	
Final Exam Form				X

***Subjects should be informed not to use ocular lubricants during the study.**

7.2. Detailed Study Procedures

VISIT 1

Subjects must arrive at visit having worn their habitual contact lenses for at least 1 hour.

Visit 1: Screening and Baseline with Habitual lenses		
Step	Procedure	Details
1.1	Statement of Informed Consent	Each subject must read, understand, and sign the Statement of Informed Consent before being enrolled into the study. The Principal Investigator or his/her designee conducting the informed consent discussion must also sign the consent form. Note: The subject must be provided a signed copy of this document.
1.2	Demographics	Record the subject's date of birth, gender, race and ethnicity.
1.3	Medical History and Concomitant Medications	Questions regarding the subjects' medical history and concomitant medications.
1.4	Habitual Lenses	Questions regarding the subject's habitual lens type and parameters.
1.5	Eligibility after Screening	All responses to Screening Inclusion Criteria questions must be answered "yes" and all responses to Exclusion Criteria must be answered "no" for the subject to be considered eligible.
Visit 1: Baseline with Habitual lenses		
Step	Procedure	Details
1.6	Entrance Visual Acuity	Record the distance Snellen visual acuity (OD, OS, and OU) to the nearest letter with their habitual lens correction in place. Subjects must read the smallest line until at least 50% of the letters are read incorrectly.

1.7	Electronic LogMAR VA with habitual lenses	
Perform monocular distance Electronic LogMAR visual acuity test at a 4-meter distance OD and OS under the following conditions:
 
 1. bright illumination (e.g., >400 lux), high luminance with low contrast charts (HLLC); 2. dim illumination (e.g., <2.5 lux), low luminance, with high contrast charts (LLHC); 	M&S Work aid [REDACTED]
1.8	qCSF with habitual lenses	
Perform monocular distance contrast sensitivity test with qCSF.
 
Contrast sensitivity will be tested within the spatial frequency range of 1.5 to 18 cpd for the qCSF method.
 
Area Under the LogCSF (AULCSF) and CSF Acuity will also be collected.
	qCSF Work aid
1.9	TFI with habitual lenses	Collect images	TFI Work aid
1.10	Remove Lenses	Have subject remove their habitual lenses and store in a case with solution. Provide a case if subject does not have one.	
1.11	Subjective Sphero-cylindrical Refraction (SCR) LENSES OFF	
The investigator will complete subjective sphero-cylindrical refraction and then place in a trial frame and record the resultant distance Electronic LogMAR visual acuity (OD, OS and OU) to the nearest letter.
 
High Luminance (>400 lux) High Contrast for eLogMAR
	[REDACTED]

1.12	Subjective Best Sphere Refraction LENSES OFF	
Perform subjective best sphere refraction with a phoropter (adopt the maximum plus to maximum visual acuity (MPMVA) approach and use the duo-chrome test for binocular balancing). to achieveth best corrected distance visual acuity (OD, OS, OU) to the nearest letter.
 
Place refraction in a Trial Frame and record the resultant distance electronic LogMar visual acuity.
 
High Luminance (>400 lux) High Contrast for eLogMAR
 
Note: The endpoint criterion for the duo-chrome test is the lens power at which the red and green sides of the chart appear to be equally distinct. However, if the subject's response changes from "red" to "green" with only a 0.25 D change in power and no report that the two sides appear to be equally sharp, the refraction endpoint should be the lens power that leave the red chart sharper.
	
1.13	Slit Lamp Findings	
Efron Slit Lamp Classification Scale will be used to grade the findings and determine eligibility. If no slit lamp finding is noted on the EDC form it is considered as a zero "0" grade for all observations listed. If any of these slit lamp findings are Grade 3 or higher, the subject may not continue at this time, but may return up to one additional time to determine eligibility. If discontinued a final examination must be completed.
 
Should the clearance of the fluorescein need to be expedited, preservative-free rewetting drops may be instilled.
	Workaid: Efron Grading Scale Guideline
1.14	Eligibility after Baseline	All responses to Inclusion Criteria questions must be answered "yes" and all responses to Exclusion Criteria questions must be answered "no" for the subject to be considered eligible.	
1.15	Exit Distance Visual Acuity	Record the distance Snellen visual acuity with the subject's habitual lenses (OD, OS, and OU) to the nearest letter. Subjects must read the smallest line until at least 50% of the letters are read incorrectly.	
1.16		Schedule subject to return in 1-3 days	

VISIT 2

Subjects must not wear contact lenses on the day of this visit

Visit #2 – Treatment #1 (1-3 days): Electronic LogMAR Visual Acuity, qCSF, and TFI Testing

Step	Descriptor	Details	■ ■ Appendix
2.1	Adverse Events and Concomitant Medications Review	Review the subject's concomitant medications and record any changes from the previous study visit. Record any adverse events or medical history changes from the previous study visit.	Adverse Events and Concomitant Medications Review
2.2	Visual Acuity	Record the distance Snellen visual acuity with the subject's spectacles, if applicable (OD, OS, and OU) to the nearest letter. Subjects must read the smallest line until at least 50% of the letters are read incorrectly.	■ ■
2.3	Slit Lamp Findings **White Light***	Efron Slit Lamp Classification Scale will be used to grade the findings. Adverse events shall be documented and followed for significant slit lamp findings. If the clearance of the fluorescein needs to be expedited, preservative-free rewetting drops may be instilled.	Workaid: Efron Grading Scale Guideline
2.4	Continuance	Determine whether the subject is eligible to continue in the study based on the examination findings.	

Visit 2: Treatment #1		
Step	Procedure	Details
2.5	Lens/Test Treatment Information	Assign the treatment lens based on the randomization scheme. Use the Visit 1 refraction assessment: Contact lens : Select the lens power based on subjective best sphere refraction. or Trial Frames : Use the best corrected spherocylindrical refraction NB: The trial frame best corrected refraction treatment's vertex distance (mm) and PD(mm) should be adjusted by the investigator for powers greater than -4.00.

2.6	Lens insertion (if applicable)	
The investigator or the subject inserts the study lenses (if applicable). Record the time of lens insertion.
 
Check for lens damage under the slit lamp before proceeding with lens settling and replace damaged lenses, if applicable.
 
Use the solution from the blister pack to rinse the lenses if needed. New pair of lenses will need to be dispensed if a blister pack solution is unavailable.
	
2.7	Lens settling (if applicable)	Allow the study lenses to settle for a minimum of 15 minutes.	
2.8	Subjective Lens Fit Assessment (if applicable)	
The lens fit will be judged to be either acceptable or unacceptable by the investigator based on centration, movement and other fitting characteristics.
 
An unacceptable fit is deemed by one of the following criteria:
 
 • limbal exposure at primary gaze or with extreme eye movement; • edge lift; • excessive movement in primary and up gaze; or • insufficient movement in all three of the following conditions: primary gaze, up gaze, and Josephson push up. 
Note: if lens fit is unacceptable subject will be discontinued from the study.
	 
2.9	Over refraction	Adjust the contact lens or trial frame lens power if the subject's best sphere over-refraction is not plano. Will allow +/-0.25 in the over refraction for -6.00 to -9.00.	
2.10	Lens Power Modification (if applicable)	
For each study lens power modification, repeat steps 2.5 - 2.9
 
Up to three power modifications are allowed.
	
2.11	Distance electronic LogMAR Visual Acuity	
Perform monocular distance Electronic LogMAR visual acuity test at a 4-meter distance OD and OS under the following conditions:
 
 1. bright illumination (e.g., >400 lux), high luminance with low contrast charts (HLLC) 2. dim illumination (e.g., <2.5 lux), low luminance (using neutral density filter), with high contrast charts (LLHC); 	M&S Work Aid 

2.12	qCSF	Perform monocular distance contrast sensitivity test with qCSF. Contrast sensitivity will be tested within the spatial frequency range of 1.5 to 18 cpd for the qCSF method. Area Under the Log CSF (AULCSF) and CSF Acuity will also be collected.	qCSF Work aid
2.13	TFI	Collect images	TFI Work aid
2.14	Lens Removal	Discard lenses after use	
2.15	Slit Lamp (if applicable)	Efron Slit Lamp Classification Scale will be used to grade the findings. Adverse events shall be documented and followed for significant slit lamp findings. If the clearance of the fluorescein needs to be expedited, preservative-free rewetting drops may be instilled.	Workaid: Efron Grading Scale Guideline
2.16	Exit VA	Record the exit distance Snellen visual acuity OD, OS, OU with habitual condition.	████████
2.17		Schedule subject to return in 1-3 days	

VISIT 3

Subjects must not wear contact lenses on the day of this visit

Visit #3 – Treatment #2 (1-3 days): SCR Electronic LogMAR Visual Acuity, QCSF			
Step	Descriptor	Details	████████ Appendix
3.1	Adverse Events and Concomitant Medications Review	Review the subject's concomitant medications and record any changes from the previous study visit. Record any adverse events or medical history changes from the previous study visit.	Adverse Events and Concomitant Medications Review
3.2	Visual Acuity	Record the distance Snellen visual acuity with the subject's spectacles, if applicable (OD, OS, and OU) to the nearest letter. Subjects must read the smallest line until at least 50% of the letters are read incorrectly.	████████

3.3	Slit Lamp Findings ***White Light***	Efron Slit Lamp Classification Scale will be used to grade the findings. Adverse events shall be documented and followed for significant slit lamp findings. If the clearance of the fluorescein needs to be expedited, preservative-free rewetting drops may be instilled.	Workaid: Efron Grading Scale Guideline
3.4	Continuance	Determine whether the subject is eligible to continue in the study based on the examination findings.	

Visit 3: Treatment #2		
Step	Procedure	Details
3.5	Lens/Test Treatment Information	
Assign the treatment lens based on the randomization scheme.
 
Use the Visit 1 refraction assessment:
 
Contact lens: Select the lens power based on subjective best sphere refraction.
 
or
 
Trial Frames: Use the best corrected sphero-cylindrical refraction
 
NB: The trial frame best corrected refraction treatment's vertex distance (mm) and PD(mm) should be adjusted by the investigator for powers greater than -4.00.

3.6	Lens insertion (if applicable)	
The investigator or the subject inserts the study lenses (if applicable). Record the time of lens insertion.
 
Check for lens damage under the slit lamp before proceeding with lens settling and replace damaged lenses, if applicable.
 
Use the solution from the blister pack to rinse the lenses if needed. New pair of lenses will need to be dispensed if a blister pack solution is unavailable.

3.7	Lens settling (if applicable)	Allow the study lenses to settle for a minimum of 15 minutes.

3.8	Subjective Lens Fit Assessment (if applicable)	
The lens fit will be judged to be either acceptable or unacceptable by the investigator based on centration, movement and other fitting characteristics.
 
An unacceptable fit is deemed by one of the following criteria:
 
 • limbal exposure at primary gaze or with extreme eye movement; • edge lift; • excessive movement in primary and up gaze; or • insufficient movement in all three of the following conditions: primary gaze, up gaze, and Josephson push up. 
Note: if lens fit is unacceptable subject will be discontinued from the study.
	
3.9	Over refraction	Adjust the contact lens or trial frame lens power if the subject's best sphere over-refraction is not plano. Will allow -0.25 in the over refraction for -6.00 to -9.00.	
3.10	Lens Power Modification (if applicable)	For each study lens power modification, repeat steps (3.5 – 3.9). Up to three power modifications are allowed.	
3.11	Distance electronic LogMAR Visual Acuity	Perform monocular distance Electronic LogMAR visual acuity test at a 4-meter distance OD and OS under the following conditions: 
 1. bright illumination (e.g., >400 lux), high luminance with low contrast charts (HLLC) 2. dim illumination (e.g., <2.5 lux), low luminance (using neutral density filter), with high contrast charts (LLHC); 	M&S Work Aid [REDACTED]
3.12	qCSF	Perform monocular distance contrast sensitivity test with qCSF. Contrast sensitivity will be tested within the spatial frequency range of 1.5 to 18 cpd for the qCSF method. Area Under the Log CSF (AULCSF) and CSF Acuity will also be collected.	qCSF Work aid
3.13	TFI	Collect images	TFI Work aid
3.14	Lens Removal	Discard lenses after use	

FINAL EVALUATION

The final evaluation will ordinarily take place immediately following the last scheduled follow-up visit per the study protocol. It may also take place at any point the subject discontinues the study or is terminated from the study.

Final Evaluation			
Step	Procedure	Details	
F.1	Final Exam Form	Indicate if the subject completed the study successfully. If subject discontinued from the study indicate the reason.	
F.2	Subjective spherocylindrical Refraction	Perform bare-eye subjective spherocylindrical refraction with a phoropter and record the best corrected distance Snellen visual acuity to the nearest letter (OD, OS, OU).	
F.3	Exit Slit Lamp Biomicroscopy	Efron Slit Lamp Classification Scale will be used to grade the findings and determine eligibility. If no slit lamp finding is noted on the EDC form it is considered as a zero "0" grade for all observations listed. After the slit lamp examination, at the discretion of the Investigator, rinse the subject's eyes thoroughly with preservative-free saline.	Workaid: Efron Grading Scale Guideline

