1. INTRODUCTION AND BACKGROUND

██████████ was able to demonstrate statistically significant differences in LogMAR VA and quick Contrast Sensitivity function (qCSF) for ACUVUE OASYS® Brand Contact Lenses 1-Day with HydraLuxe™ Technology when compared to a positive Control (ACUVUE OASYS® Brand Contact Lenses 1-Day with HydraLuxe™ Technology with an added +0.25 D) and to ACUVUE OASYS®. This study will continue the investigation looking into the visual performance of ACUVUE OASYS® 1-Day compared to spectacles, in a myopic population including high myopes, through electronic LogMAR VA (eVA), qCSF as well as other observations such as tear film interferometry (TFI).

The qCSF was developed by Adaptive Sensory Technology© which uses the AST Sentio Platform for clinical testing of contrast sensitivity.² It incorporates the qCSF algorithm aimed to improve usability and comfort, while maintaining laboratory-grade precision of the test. The AST Sentio Platform is a low-risk, class I, 510(k)-exempt device that has received CE marking for marketing in Europe and is currently in the process of obtaining FDA clearance in the United States. This newer technique was chosen for this clinical trial due to its ability to deliver precise, accurate results under different conditions within a very short time (~40 minutes) compared to existing techniques.

Tear film interferometry with contact lenses on and off the eyes will also be investigated here, in an attempt to determine the feasibility of a tear film interferometry metric correlation to visual acuity.

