1.5. Relevant Literature References and Prior Clinical Data Relevant to Proposed Clinical Study

2. STUDY OBJECTIVES, ENDPOINTS AND HYPOTHESES

2.1. Objectives

- The primary objective of the study is to assess electronic LogMAR Visual Acuity under high luminance, low contrast (HLLC) and low luminance high contrast (LLHC) in subjects randomly fit with:
 - (i)AO1D, and
 - (ii) their best corrected spherocylindrical refraction (Trial Frame)
- The secondary objective is to compare Contrast sensitivity as measured through the qCSF (by AST Sentio Platform's technology) for the same 2 testing conditions listed above.
- Other Objectives: Obtain tear film interferometry measurements with and without contact lens wear. Investigate feasibility of tear film interferometry metric correlation to visual acuity.

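### The 0.25 D over-refraction tolerance in steps 2.9 and 3.9 is not limited to AO1D, so the trial-frame control may be tested while not best corrected

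*Combined protocol and SAP*

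**What the plan says.** Section 2.1 defines the control condition as "their best corrected spherocylindrical refraction (Trial Frame". The primary hypothesis in Section 2.3 uses the same comparator, with a margin of 0.05 logMAR. At Visits 2 and 3 the trial frame starts from the Visit 1 refraction (steps 2.5 and 3.5): "Use the best corrected spherocylindrical refraction". The same steps tell the investigator to adjust vertex distance and PD for powers beyond -4.00.

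Power is then checked by over-refraction. Steps 2.9 and 3.9 open with the same instruction, which covers both conditions, and then give a tolerance. Step 2.9 reads: "Adjust the contact lens or trial frame lens power if the subject's best sphere over-refraction is not plano. Will allow +/-0.25". The tolerance in full is "Will allow +/-0.25 in the over refraction for -6.00 to -9.00" at Visit 2 and "Will allow -0.25 in the over refraction for -6.00 to -9.00" at Visit 3. Neither sentence says which condition it applies to.

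Table 1 (Section 6.1) gives AO1D in 0.25 D steps to -6.00 and then "6.50 to -9.00 in .50D steps". It gives no power step for the control. Section 14.5 declares non-inferiority if the upper 95% confidence limit of the difference is below 0.05, and superiority if it is below 0.

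**The concern.** A control described as best corrected should not be tested with a residual that the examiner has found and left in place. A remaining minus over-refraction means the eye is under-corrected and blurred at distance. If this happens in SCR, the control's logMAR rises and AO1D minus SCR falls relative to the comparison that the objective names. A lower difference helps AO1D under both rules in Section 14.5.

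The eyes affected are the high myopes, whom Section 1 says the study means to include. Section 1 also reports that a prior study found statistically significant differences in LogMAR VA and qCSF for AO1D against comparators that included AO1D "Technology with an added +0.25 D". The sponsor's own background therefore treats a quarter dioptre as detectable, although it gives no effect size.

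**Working it through.** **1. Does the reason for a tolerance reach the trial frame?** From -6.00 to -9.00 in 0.25 D steps there are (9.00 - 6.00)/0.25 + 1 = 13 powers. AO1D lacks six of them: -6.25, -6.75, -7.25, -7.75, -8.25 and -8.75. A 0.25 D residual can therefore be unavoidable with AO1D. Nothing in the documents makes it unavoidable in a trial frame.

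**2. The plan's own figures.** Section 14.2 gives 24 eyes (true difference 0) and 63 eyes (true difference 0.02) for 90% power, with SD 0.08 and margin 0.05. A paired non-inferiority t-test (non-central t, SD of the difference 0.08) returns exactly 24 and 63 at one-sided 0.05. At one-sided 0.025, which matches the 95% interval in Section 14.5, it returns 29 and 77. The steps below use one-sided 0.025, because that is the decision rule.

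**3. Precision.** There are 42 completers with 2 eyes each, so 84 eyes. Taking the stated intraclass correlation of 0.5 as the correlation between a subject's two eyes, the effective number is 84/(1 + 0.5) = 56. SE = 0.08/√56 = 0.0107, with 55 degrees of freedom.

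**4. Size of an SCR-only bias.** Three inputs are assumptions that the documents do not supply:
- share of eyes in -6.00 to -9.00: 20% to 50%
- share of those with an uncorrected -0.25 D in SCR and none in AO1D: 25% to 50%
- acuity lost per 0.25 D: 0.02 to 0.05 logMAR

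Bias = share × frequency × loss.
- Minimum: 0.20 × 0.25 × 0.02 = 0.001
- Maximum: 0.50 × 0.50 × 0.05 = 0.0125

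**5. Effect on the decision.** The probability that the upper limit falls below 0.05 comes from the non-central t with non-centrality (0.05 - true difference + bias)/SE.

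| SCR-only bias (logMAR) | True difference 0.05 (error) | True difference 0.02 (power) |
|---|---|---|
| 0 | 2.5% | 78.7% |
| 0.001 | 3.1% | 81.3% |
| 0.005 | 6.7% | 89.5% |
| 0.0075 | 10.2% | 93.1% |
| 0.0125 | 20.9% | 97.4% |

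**6. When both conditions use the tolerance.** The observed shift in AO1D minus SCR is share × loss × (AO1D frequency - SCR frequency).
- Equal frequency: shift 0, error 2.5%.
- Residual only in AO1D, in half of eligible eyes, with share 50% and loss 0.05: shift +0.0125. The error at the margin falls to 0.1%, and power at a true difference of 0.02 falls from 78.7% to 36.3%.

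The sign of the observed shift therefore depends on which condition carries more residual. The documents do not settle that.

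**The case against.** A reader might infer that the tolerance biases the trial in favour of AO1D. The documents do not support that. The sentence that reaches the trial frame reaches the contact lens too, and AO1D's missing powers make a residual at least as likely there. One can argue that an AO1D residual belongs to the question (the lens as supplied) while an SCR residual does not. But the documents do not state that estimand, and the tolerance would also let AO1D keep a residual that an available power could remove. What remains is narrower: an SCR residual departs from the stated comparator whatever happens in AO1D. Equal residuals would give no net shift, but the result would still not be a comparison with best correction.

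The sponsor may also have meant the tolerance for the lens only. The first sentence orders the trial frame to be adjusted, and the tolerance range lies where AO1D moves to 0.50 D steps. That reading is plausible and agrees with the objective, but the text does not say it.

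The vertex adjustment in steps 2.5 and 3.5 covers the whole affected range and makes SCR residuals less likely. It does not exclude them. If a 4 mm vertex difference were missed (an assumed figure), effective power would shift by about 0.25 D at -8.00: -8.00/1.032 = -7.75, or -8.00/0.968 = -8.26. The shift can go either way, and only the minus residual has been argued to blur. The plus residual, allowed at Visit 2 only, has not been shown to cost acuity.

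Finally, the error rates rest on three stacked assumptions, and 20.9% needs all three at their maximum. Significance in the prior study does not establish a loss of 0.02 to 0.05 logMAR here.

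**Conclusion.** The point holds as an inconsistency in how the comparator is defined. The objective and hypothesis require a best-corrected control, while steps 2.9 and 3.9 as written allow an SCR eye in -6.00 to -9.00 to be tested with a 0.25 D residual, with no reason given that applies to a trial frame. Relative to a best-corrected control, acuity lost in SCR can only make the two Section 14.5 rules easier to meet.

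A net advantage to AO1D in the observed data is not shown. Its direction and size are unknown because AO1D carries the same tolerance. The range of 3.1% to 20.9%, against 2.5%, describes an SCR-only residual under the stated assumptions. It is a sensitivity range and does not estimate what will happen.

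The two steps also differ in sign (+/-0.25 at Visit 2, -0.25 at Visit 3). Randomised sequence balances visit across conditions on average, so this alone favours neither, but it should be reconciled in the same edit. The change is worth making because it is small and protects the comparator.

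**What to change.** 1. Reconcile steps 2.9 and 3.9 with Sections 2.1 and 2.3 so that the tolerance does not extend to the SCR comparator, and resolve the difference between the two visits.
2. Record the final over-refraction for each eye and condition. Neither step asks for this. The eCRF is not among the documents, so a field may already exist.
3. Add a sensitivity analysis to Section 14.5. It should either adjust for the residual over-refraction in both conditions, or exclude both conditions of any eye whose final SCR over-refraction was not plano. Dropping the SCR measurement alone would be a one-sided exclusion after randomisation. It would leave AO1D eyes unpaired and could itself bias the difference.

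The cost is a sentence in each of two steps, at most one data field, one extra model and an occasional additional trial-lens change in a high-myope SCR visit. The result may be slightly less favourable to AO1D. If testing is already complete and the over-refraction was recorded, item 3 can still be done.
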